## 10.6 Safety Analyses

Safety data will be summarized for subjects who received  $\geq 1$  dose of active investigational product by the actual treatment received in the double-blind period (any subject randomized to ALN arm who incorrectly receives  $\geq 1$  dose of romosozumab will be analyzed as receiving romosozumab).

Safety data for the double-blind period and for primary analysis period will be summarized separately using analysis set defined in [Section 7.5](#). Safety data will also be summarized for the overall study period (at final analysis) using analysis set defined in [Section 7.5](#).

**A listing of adverse events will be prepared for subjects who did not received any active dose of investigational product in the 12-month of double-blind period. A listing of adverse events occurring after double-blind period will be prepared for subjects**

who received at least one **active** dose of investigational product in the 12-month of double-blind period, remained on study in the open-label period without open-label alendronate exposure.

### 10.6.1 Adverse Events

The Medical Dictionary for Regulatory Activities (MedDRA) version 19.1 or later will be used to code all adverse events to a system organ class and a preferred term for the 12-month double-blind period, the primary analysis period (at the primary analysis) , and the overall study period (at the final analysis). Adverse events will be summarized in the double-blind period, in the primary analysis study period (at the primary analysis), and overall study period (at the final analysis) for all subjects who receive at least one dose of investigational product in the double-blind period. The subject incidence rates for the primary study and overall study period will include all events that occurred in the double-blind period, and in addition, all events that occurred in the open-label period for those subjects who received at least one dose of open-label ALN.

All adverse event tables will be summarized by actual treatment group. The subject incidence of adverse events will be summarized for all treatment-emergent, serious, treatment-related, serious treatment-related, those leading to withdrawal of study, leading to withdrawal of investigational product, fatal, and of special interest. Subject incidence of special interest adverse events will also be summarized according to their categories.

Subject incidence of all treatment-emergent, serious, treatment-related, serious treatment-related, those leading to withdrawal of study, leading to withdrawal of investigational product, and fatal adverse events will be tabulated by system organ class and preferred term in descending order of frequency. Subject incidence of all treatment-emergent adverse events will be tabulated by system organ class, high-level group term, and preferred term in descending order of frequency as well as by preferred term.

Summaries of treatment-emergent adverse events occurring in at least 5% of the subjects and serious treatment-related adverse events occurring in at least 0.1% of the subjects will be provided by preferred term in descending order of frequency.

Treatment-emergent adverse events occurring in at least 2% of the subjects and also

have a >1% difference than ALN will also be summarized by preferred term in descending order of frequency.

Subgroups group analyses for age strata (< 75, ≥ 75 years) will be presented by system organ class and preferred term in descending order of frequency.

In addition, subject incidence rates of adverse events corresponding to preferred terms of events of interest of hypocalcemia, injection site reactions, potentially related to hypersensitivity (Standardized MedDRA Query [SMQ], narrow scope), malignant or unspecified tumor (SMQ, narrow scope), hyperostosis, osteoarthritis, adjudicated adverse events of osteonecrosis of the jaw, and atypical femoral fracture will be provided.

Unless otherwise specified, there is no planned statistical testing in the safety analyses.

#### **10.6.2 Osteonecrosis of the Jaw Adjudication**

The events of osteonecrosis of the jaw (ONJ) which occurred in the study will be adjudicated and summarized. All potential events of ONJ identified through a pre-defined search of the MedDRA terms will be submitted to the Osteonecrosis of the Jaw Adjudication Committee for blinded review and adjudication. The committee will determine whether the event meets the case definition criteria for ONJ.

Number of adjudicated positive ONJ events will be summarized.

#### **10.6.3 Adjudicated Positive Cardiovascular Events**

All deaths and potential cardiovascular-related serious adverse events will be submitted to an external independent committee comprised of experienced cardiologists for blinded adjudication. The committee will adjudicate the events and determine whether the event is cardiovascular in nature.

Baseline cardiovascular risk factors will be summarized descriptively. These risk factors are defined as age (≥ 75, < 75), smoking history, and other clinical history including hypertension, diabetes, cardiovascular disease, and hypercholesterolemia. The cardiovascular risk factors of history of hypertension, diabetes, cardiovascular disease, and hypercholesterolemia will be identified based on the Medical & Surgical History eCRF based on MedDRA version 19.1. The SMQ for Hypertension, the SMQ for Hyperglycaemia, and the System Organ Classes of Cardiac Disorders and Vascular

Disorders will be used to identify preferred terms associated with hypertension, diabetes and cardiovascular disease, respectively. The Dyslipidaemia SMQ will be used to identify history of hypercholesterolemia, excluding terms associated with conditions of low cholesterol or increased high-density lipoprotein.

Only events confirmed positive by the adjudication committee to meet cardiovascular event definition criteria will be included for analyses. Adjudicated cardiovascular events of death, cardiac ischemic event, cerebrovascular event, non-coronary revascularization, heart failure and peripheral vascular events not requiring revascularization will be summarized using subject incidence rates, odds ratios and 95% confidence intervals. No statistical tests will be performed.

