### **3.4 Estimated Study Duration**

#### **3.4.1 Study Duration for Participants**

Study duration is event-driven, ie, the end of study visits will occur when nonvertebral fracture events have been confirmed by the central imaging vendor for at least 440 subjects, unless the primary analysis demonstrates superiority of romosozumab treatment for nonvertebral fracture risk reduction (see [Section 10.2](#) for details on testing strategy). Study completion constitutes either completion of primary analysis if superiority is proven for nonvertebral fractures or when at least 440 subjects have experienced a nonvertebral fracture. Enrollment is expected to take approximately 34 months; however, recruitment is competitive and will stop after approximately 4,000 subjects are enrolled.

The estimated study duration for an individual subject, including the screening period, is 25 to 59 months (if study completion is achieved at primary analysis) or 37 to 71 months (if study completion is achieved when at least 440 subjects have experienced a nonvertebral fracture), based on projected enrollment and estimated fracture rates.

However, actual study duration for individual subjects may be longer, depending on actual enrollment and observed fracture rates.

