#### Subject Incidence Rate for Adverse Events

The subject incidence rate for a given event in a given time period (double-blind period, primary analysis period, or overall study period) is defined as the number of subjects with  $\geq 1$  reported occurrence of the event divided by the number of subjects who are at risk for having the event in the beginning of the given time period. For subjects with multiple occurrences of the same event in a given period, the event will only be counted once per subject.

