### **Subject Years On-Study in Primary Analysis Period**

Defined for a given subject as the number of days between the first dose date to end of primary analysis period date, inclusive, divided by 365.25 (ie,  $[\text{End of Primary Analysis Period Date} - \text{First Dose Date} + 1] / 365.25$ ). The subject years on study will be summed over all subjects within a treatment group. For subjects who never received a dose of investigational product, the randomization date will be used.

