### **Time to First Event in Double-blind Period**

Time to event is calculated as the elapsed time interval in days between the occurrence date of the event of interest or censorship and the reference date:

$$\text{Time Interval} = \text{Date of the Event or Censorship} - \text{Reference Date} + 1$$

Note for fracture endpoints, the date of event is the date that confirms the fracture provided by the central imaging reader (eg, date of x-ray used by the central imaging vendor to verify the fracture, or surgical report or discharge summary if x-ray date is not available). For adverse events, nonvertebral fractures, and other events, which can be assessed at any time, subjects who did not have any event will be censored on the date of last evaluation for the event, which is the End of Double-blind Study Period; for vertebral fractures, which have to be identified on scheduled assessments, subjects who did not have any event will be considered censored at the last post-baseline assessment or day 1 if there were no post-baseline assessment.

The reference date will be the randomization date for efficacy events or first dose date for safety endpoints.

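### The primary-period odds ratio for adjudicated cardiovascular events ignores time at risk, so it is unprotected if dropout, stopping of IP or open-label alendronate uptake differs by arm

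*SAP*

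**What the plan says.** SAP 10.6.3 lists the adjudicated categories (death, cardiac ischaemic event, cerebrovascular event, heart failure and others) and states that they "will be summarized using subject incidence rates, odds ratios and 95% confidence intervals". It adds "No statistical tests will be performed". SAP 6.3 defines the subject incidence rate as subjects with at least one event "divided by the number of subjects who are at risk for having the event in the beginning of the given time period", which is a proportion without person-time.

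Two periods are reported. SAP 10.6: "Safety data for the double-blind period and for primary analysis period will be summarized separately". The primary analysis period includes the double-blind year. Under SAP 7.5 and 10.6.1, events after the double-blind period enter the primary-period incidence only for women who took at least one open-label alendronate dose. Under SAP 10.6, later events in women who stayed on study without open-label alendronate go to a listing.

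SAP 6.3 also defines time to first event for safety: "The reference date will be the randomization date for efficacy events or first dose date for safety endpoints". It defines subject-years for each period: "The subject years on study will be summed over all subjects within a treatment group". Section 10.6.3 uses neither.

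Protocol 3.4.1 states that individual duration, screening included, "is 25 to 59 months" if the study completes at the primary analysis.

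**The concern.** A crude proportion treats a woman observed for 6 months and one observed for 50 months alike. If one arm is observed for less time, it collects fewer events and looks safer, even when the drugs carry the same risk.

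Randomisation does not balance what happens after it. Three routes to unequal observation are open here:

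- **Dropout.** It may differ between two different active drugs in year 1.
- **Open-label uptake.** A woman who stays on study without open-label alendronate remains in the denominator, but her later events leave the numerator.
- **Stopping of IP.** Protocol 7.9 adjudicates deaths and serious adverse events. Protocol 9.2.2 requires serious events to be reported through 30 days after the last dose, whereas 9.1.2 asks for adverse events through the end of study. Women who stop IP are asked to stay on study (8.1), so capture may end before exit.

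At stake is whether a reader can take the cardiovascular odds ratio over the longer period at face value.

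**Working it through.** **1. Follow-up range.** SAP 3.2.1 gives 34 months of enrolment and a 24-month minimum: 24 + 34 = 58 months. Protocol 3.4.1 gives 25-59 months including screening; less about 1 month, that is 24-58. The two agree.

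**2. Inputs.** Documents: 1:1 allocation, about 2,000 per arm, dropout 10% in year 1 and 8% per year thereafter (one figure, not given by arm). Assumptions: cardiovascular event rates of 1%, 2% and 3% per year, since the documents give none; uniform accrual; any dropout or uptake difference between arms; the double-blind period taken as one year.

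**3. Formula.** Let h be the event rate, C(t) the cumulative dropout hazard (-ln 0.90 per year in year 1, then -ln 0.92), and A(t) the share still within administrative follow-up (1 to year 2, then falling linearly to 0 at month 58).

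- Mean counted time to first event: m = integral of exp(-ht - C(t)) A(t) dt
- Crude proportion: p = h x m
- Odds ratio: [p1/(1-p1)] / [p0/(1-p0)]
- Rate ratio: (p1/m1)/(p0/m0), which is 1 under the null

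**4. Staggered entry alone.** With equal dropout and no effect, the odds ratio is 1.000 at every assumed rate. In 4,000 simulated null trials at 2% per year, its geometric mean was 0.998 (log odds ratio -0.0024, Monte Carlo standard error 0.0022), and the 95% intervals covered 95.2%. The chance difference between arms in mean administrative follow-up has standard error 34/sqrt(12) x sqrt(2/2000) = 0.31 months. With a true constant hazard ratio of 1.30 the odds ratio is 1.305-1.314; with 1.50 it is 1.509-1.527.

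**5. Dropout that differs by arm, no true effect.** The other arm keeps 10%/8%.

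| Dropout, year 1/later | OR at 1%/yr | OR at 2%/yr | OR at 3%/yr | Rate ratio |
|---|---|---|---|---|
| 8%/6% | 1.039 | 1.040 | 1.040 | 1.000 |
| 12%/10% | 0.963 | 0.962 | 0.961 | 1.000 |
| 15%/12% | 0.917 | 0.916 | 0.914 | 1.000 |
| 20%/16% | 0.840 | 0.837 | 0.834 | 1.000 |

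Worked case, 15%/12% at 2%: p0 = 0.02 x 2.8025 = 0.05605, odds 0.05938; p1 = 0.02 x 2.5783 = 0.05157, odds 0.05437; 0.05437/0.05938 = 0.916.

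**6. Open-label uptake that differs by arm, no true effect.** Suppose later events are counted in 90% of one arm and 95% of the other. At 2% per year, year 1 contributes 0.02 x (1 - exp(-0.12536))/0.12536 = 0.0188, where 0.12536 = 0.02 - ln 0.90. Later time contributes 0.05605 - 0.0188 = 0.03725. So p1 = 0.0188 + 0.90 x 0.03725 = 0.0523, p0 = 0.0188 + 0.95 x 0.03725 = 0.0542, and the odds ratio is 0.964.

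The subject-years in SAP 6.3 would not repair this. They run to the period end (or study exit) for every woman, so they are equal in both arms here, and the rate ratio on them is 0.0523/0.0542, about 0.97. With person-time stopped when counting stops, it is 1.000.

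**7. Excess confined to year 1.** A hazard ratio of 1.5 in year 1 only gives a 12-month odds ratio of 1.50-1.51 (no dropout). Over the primary period, both the odds ratio and the rate ratio are about 1.17.

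**The case against.** A reader might infer that the 24-58 month spread itself biases the cardiovascular comparison. The documents do not support that. Enrolment is concurrent and 1:1, both arms share one cut-off rule, and step 4 shows an odds ratio at the null with correct coverage.

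A reader might also infer that the plan cannot show whether an excess falls in the romosozumab year. That overlooks the separate double-blind summary, which SAP 6.1.2 caps at Study Day 396 and which matches the primary safety hypothesis about 12 months of treatment. Even with assumed year-1 dropout of 15% against 10%, mean follow-up in that year is 0.15/0.1625 = 0.923 against 0.10/0.1054 = 0.949 years, a ratio of 0.97.

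The strongest remaining objection is that the bias is hypothetical. The documents assume one dropout rate for both arms and give no reason to expect a difference. The 15%/12% scenario, with dropout 50% higher in one arm, moves the odds ratio only to 0.91-0.92. The analysis is descriptive, and an unblinded DMC reviews safety.

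All of that stands as a limit on size. It does not remove the gap: post-randomisation differences are what a crude proportion cannot absorb, and the open-label counting rule ties the numerator to a post-randomisation act.

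**Conclusion.** The plan contains no error that biases the cardiovascular comparison by design. While follow-up and event counting are balanced, the odds ratio tracks the rate ratio closely. The weakness is that the primary-period odds ratio is the only comparative measure for that period and would absorb any arm difference in dropout, stopping of IP or open-label uptake. Under the null this means about 0.96 for a modest dropout difference, 0.91-0.92 for a larger one, and about 0.96 for a five-point difference in open-label uptake. The arm that is observed less looks safer.

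These sizes rest on assumed event rates, dropout splits and uptake splits. They show sensitivity; they do not predict what this trial will find. The 12-month summary is much less exposed. The point is a cheap improvement worth making before unblinding.

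**What to change.** Add to SAP 10.6.3, for each adjudicated category and for both the double-blind and primary analysis periods:

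- Kaplan-Meier curves by arm
- a Cox hazard ratio with 95% confidence interval, stratified by age
- exposure-adjusted event rates

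Define time at risk from first dose to the first event or to the end of event counting for that woman. For the primary period, counting ends at the end of the double-blind period if she took no open-label alendronate; otherwise it ends at the earlier of end of study and end of the primary analysis period. Do not use the SAP 6.3 subject-years unchanged, because they would not match the numerator. State which of Protocol 9.1.2 and 9.2.2 governs capture of serious events after IP stops, so that the censoring date follows it.

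Keep the odds ratio and add no formal test. The cost is a few extra outputs and one derived censoring date. A single period-wide hazard or rate ratio is still diluted if an excess is confined to year 1, so timing should be read from the curves and the 12-month summary.

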#### **10.6.4 Atypical Femoral Fracture Adjudication**

The events of atypical femoral fracture (AFF) which occurred in the study will be adjudicated and summarized. All potential events of AFF identified through a pre-defined search of the MedDRA terms will be submitted to the Atypical Femoral Fracture Adjudication Committee for blinded review and adjudication. The committee will determine whether the event meets the case definition criteria for AFF.

Number of adjudicated positive AFF events will be summarized.

#### **10.6.5 On Study Cancer**

Number and percentage of subjects who reported new malignancy on study will be summarized by cancer category and cancer status.

#### **10.6.6 Injection Site Reaction**

The number of episodes of injection site reaction, duration, nature (concomitant versus recurrent) and severity will be summarized during the double-blind study period. The time (in days) to first injection site reaction during the double-blind study period will also be summarized descriptively.

#### **10.6.7 Hypersensitivity**

Subject incidence of hypersensitivity as an EOI with on-set day within 2 days since receiving any dosing of investigational product by preferred term will be provided for the double-blind study period. Similarly, the analyses will be repeated for hypersensitivity with on-set day  $> 2$  and  $\leq 7$  days since receiving any dosing of investigational product.

In addition, subject incidence of concomitant/recurrent hypersensitivity EOs, hypersensitivity leading to investigational product discontinuation, and hypersensitivity leading to study discontinuation will be provided by preferred term for the double-blind study period.

#### **10.6.8 Tumor Necrosis Factor Mediated Inflammatory Diseases**

Subject incidence rates of adverse events corresponding to a Amgen search strategy of preferred terms for tumor necrosis factor (TNF) mediated inflammatory diseases will be provided using the safety analysis set for all subjects, subjects with prior history of TNF disease, and subjects without prior history of TNF disease.

#### **10.6.9 Laboratory Test Results**

Subjects with missing data for a scheduled visit will not contribute to the safety tabulations for that time point (no imputation). Descriptive statistics for the actual value at each visit and the change from baseline at each post-baseline visit during the study period will be summarized. Figures showing central tendency and dispersion of the actual values and/or changes from baseline of select laboratory parameters (calcium corrected by albumin, phosphorus, magnesium and alkaline phosphatase) during the double-blind period will be provided. Above summary statistics and figures will also be done for percent change from baseline in calcium corrected by albumin, phosphorus, magnesium, and alkaline phosphatase. Visit windows will be used for these summaries as described in [Section 13.1.1](#)

Laboratory parameters will be summarized showing the shift from baseline to the most extreme post-baseline value between baseline and the end of double-blind period based on Common Terminology Criteria for Adverse Events v3.0 (CTCAE). Subject incidence of most extreme post-baseline calcium corrected by albumin decrease grade will also be summarized. The percentages of subjects with laboratory toxicities  $\geq$  grade 2 CTCAE will be summarized. In addition, subject listings of grades 3 and 4 laboratory values will be provided.

Drug-induced liver injury will be assessed by evaluating subjects for Hy's Law criteria in the double-blind period and in the primary analysis study period. Hy's law lab value criteria is defined as aspartate amino transferase or alanine amino transferase  $> 3$  times upper limit of normal (ULN), total bilirubin  $> 2$  times ULN, and alkaline phosphatase  $< 2$  times ULN assessed within 7 days. Subjects who meet these lab criteria on study will

be further evaluated to assess whether there exist underlying conditions or concomitant medications which can explain the elevation in laboratory analytes.

Summaries of abnormal laboratory values, including summaries of shifts, worst post-baseline calcium, and evaluation of potential Hy's law cases will be summarized in the double-blind period and in the primary analysis period for all subjects who receive at least one dose of investigational product in the double-blind period. The subject incidence rates for the 24-month study period will include all laboratory measurements collected in the double-blind period, and in addition, all laboratory measurements collected in the open-label period for those subjects who received at least one dose of open-label alendronate.

#### **10.6.10 Vital Signs, Height, Body Weight, and BMI**

Descriptive statistics of actual values and changes from baseline in vital signs (systolic and diastolic blood pressure, heart rate, and temperature), body weight, and BMI will be presented by scheduled visit. Height, which is analyzed as an efficacy endpoint, will be summarized as well using the safety analysis set.

#### **10.6.11 Anti-Romosozumab Antibody**

Immunogenic response during the study will be described by tabulating the numbers and percentages of subjects who tested positive (binding and neutralizing) for anti-romosozumab antibodies in subjects receiving  $\geq 1$  dose of romosozumab at each visit and at any visit during study. Analysis will be performed using safety analysis set defined in [Section 7.5](#). Subjects who test positive for either binding or neutralizing antibodies against romosozumab will be interpreted as persistently positive if the antibody status remains positive throughout the last time point tested. Subjects who test positive for binding antibodies against romosozumab will be interpreted as transient positive if the binding antibody status was negative at the subject's last time point tested within the study period. Subjects who test positive for neutralizing antibodies against romosozumab will be interpreted as transient positive if the neutralizing antibody status was negative at the subject's last time point tested within study period.

If a subject tests positive for antibodies against romosozumab, the relationship between the presence of antibodies, adverse events, concomitant medications, and bone mineral density will be evaluated; the immunogenic response will be listed by subject and study day along with the serum romosozumab levels if available. Note that the serum

romosozumab levels are only collected on subjects who participate in the sub-study. The subject incidence of injection site reaction EOs, hypersensitivity EOs, and adverse events corresponding to the MedDRA high level group term of autoimmune disorders will be provided by binding and neutralizing anti-romosozumab antibody status.

